14.2 Description of analysis sets

14.2.1 Safety analysis set

All patients who commence chemoimmunotherapy

14.2.2 Efficacy analysis set

The primary analyses will be performed on the intention to treat population, i.e. all eligible patients who are randomized. Secondarily, we will analyze patients who have received a minimum of three courses of chemoimmunotherapy (both arms) plus TRT (experimental arm) (per protocol population).

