7.3 Withdrawal of patients from study treatment and/or study

7.3.1 Permanent discontinuation of chemotherapy and durvalumab

Discontinuation of study treatment, for any reason, does not impact the patient's participation in the study. A patient who decides to discontinue IP should be asked about the reason(s) for discontinuation and the presence of any AE. The patient should continue attending subsequent study visits, and data collection should continue according to the study protocol. If the patient does not agree to continue in-person study visits, a modified follow-up must be arranged to ensure the collection of endpoints and safety information. This follow-up could be a telephone contact with the patient, a contact with a relative or treating physician, or information from medical records. The approach taken should be recorded in the medical records. A patient who agrees to modified follow-up is not considered to have withdrawn consent or to have withdrawn from the study.

Patients who permanently discontinue study treatment for other reasons than objective RECIST disease progression should be followed according to the study schedule similar to patients who are on study treatment.

All patients will be followed for survival until the end of the study. Patients who decline to return to the site for evaluations should be contacted by telephone if they agree.

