7.3.2 Lost to follow-up

Patients will be considered lost to follow-up only if no contact has been established by the time the study is completed, such that there is insufficient information to determine the patient's status at that time. Investigators should document attempts to re-establish contact with patients.

In order to support key end points of PFS and OS analyses, the survival status of all patients in the full analysis and the safety analysis sets should be re-checked, this includes those patients who withdrew consent or are classified as "lost to follow-up". For patients lost to follow-up, site personnel should check hospital records, the patients' current physician, and a publicly available death registry (if available) to obtain survival status.

If a patient has actively withdrawn consent to the processing of their personal data, the survival status of the patient can be obtained by site personnel from publicly available death registries (if available) where it is possible to do so under applicable local laws to obtain a current survival status.

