9.1 Patient enrollment and randomization

9.1.1 Procedures for randomization

After patients are assigned a study ID and registered in the CRF, investigators randomize patients using the randomization module in the CRF. Patients will be randomized 1:1 in blocks of various sizes to receive chemo-immunotherapy alone or chemo-immunotherapy plus TRT stratifying for presence of liver metastases (yes vs. no), and presence of brain metastases (yes vs. no). The study is open label, and patients and investigators will know the results of the randomization. They will not, however, know the results of previous randomizations or the block sizes.

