9.1.2 Procedures for handling patients incorrectly enrolled

Patients who are incorrectly enrolled and/or randomized will be discussed with the Chief Investigator before deciding whether the patient should be withdrawn. If there has been a major protocol violation, the patient will be withdrawn from the study.

10. Restrictions during the study and concomitant treatment(s)

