11.1.5 End of treatment

Assessments for patients who have completed durvalumab treatment and achieved disease control or have discontinued durvalumab due to toxicity in the absence of confirmed progressive disease, and for those who have progressed are provided below the schedule of events on page 11.

All patients will be followed for survival until the end of the study regardless of further treatments, or until the sponsor ends the study.

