14.4 Determination of sample size

[figure not shown]
The sample size calculation assumes an accrual period of 30 months and that the primary survival analysis is performed 14 months after last patient entry. Additional survival analyses will be performed 2, 3, 4 and 5 years after last patient entry. All patients will be followed for a maximum of 5 years when the final survival

analysis will be performed.

Furthermore, the calculation is based on a constant hazard ratio of 0.65, corresponding to median survival times of 13.10 months for the control group and 20.02 months for the experimental group, and 1-year survival rates of 53% in the control group and 66% in the experimental group. This effect was selected as an effect of clinical relevance and an effect of this magnitude might be anticipated if there is a synergistic effect of combining radiotherapy with durvalumab.

The criterion for significance (alpha) has been set at 5%. The test is

2-tailed, which means that an effect in either direction will be interpreted. For this study design, alpha and tails, the population effect size described above, and to have power of 80% to yield a statistically significant result, 128 patients are required in each treatment group.

Enrolment will continue until 128 or more patients in the control arm have completed minimum three chemo-immunotherapy courses, and minimum 128 patients in the experimental group have completed minimum three chemo-immunotherapy courses plus TRT of 30 Gy. We expect a loss to follow-up and inability to complete three courses (plus TRT in the experimental group) of maximum 15% and estimate that we need to enroll a total of 302 patients.

All eligible patients who are randomized will be included in the primary efficacy analyses (ITT-population). All patients who commence chemo-immunotherapy will be included in the toxicity analyses. In addition, we will perform analyses of the patients who complete minimum three chemo-immunotherapy courses (and TRT in the experimental arm) (per protocol population). The sample size calculation was performed using SPSS Sample Power v3.

15. Ethical and regulatory requirements

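### The primary set is labelled intention to treat but is restricted to eligible randomised patients, so an open-label trial can drop patients from its primary survival analysis after allocation is known

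*Protocol*

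**What the plan says.** Section 14.2.2 defines the primary set: "The primary analyses will be performed on the intention to treat population, i.e. all eligible patients who are randomized". Section 14.4 and the sample-size part of the synopsis say the same: "All eligible patients who are randomized will be included in the primary efficacy analyses (ITT-population". The restriction thus appears three times, in consistent terms.

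On errors at entry, section 9.1.2 says: "Patients who are incorrectly enrolled and/or randomized will be discussed with the Chief Investigator before deciding whether the patient should be withdrawn". It continues: "If there has been a major protocol violation, the patient will be withdrawn from the study". It does not mention analysis sets, and it does not say whether such patients stay in survival follow-up.

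On blinding, section 9.1.1 says: "The study is open label, and patients and investigators will know the results of the randomization".

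On survival data, section 7.3.1 says "All patients will be followed for survival until the end of the study", and section 11.1.5 says "All patients will be followed for survival until the end of the study regardless of further treatments". Section 7.3.2 asks that "the survival status of all patients in the full analysis and the safety analysis sets should be re-checked", but section 14.2 defines only a safety set, the set called intention to treat, and a per-protocol set. No full analysis set is defined.

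**The concern.** Intention to treat means that every randomised patient is analysed in the arm assigned. Adding the condition of eligibility makes it a modified set. That would matter little if eligibility were settled before allocation, but section 9.1.2 expects some errors to surface after randomisation and leaves the decision to a case-by-case discussion. Nothing in the protocol limits that judgement to pre-randomisation data, blinds it to arm and outcome, or sets a deadline for it.

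The risk is that exclusions differ between arms in a way related to prognosis. One possible route lies in inclusion criterion 8, which requires a thoracic lesion that can be irradiated to 30 Gy in 10 fractions. After randomisation, radiotherapy planning takes place only in the experimental arm, so a failure of this criterion is more likely to come to light there. The protocol does not say that such a patient would be reclassified as ineligible, and section 8.3.1 keeps patients who miss TRT on chemo-immunotherapy. This is a possibility and not evidence of imbalance.

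**Working it through.** **1. The plan's own figures.** Inputs from section 14.4: HR 0.65, control median 13.10 months, 30 months of accrual, analysis 14 months after last entry, two-sided alpha 5%, power 80%, 15% loss or non-completion.

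- Deaths needed (Freedman): (1.960 + 0.842)² × (1.65/0.35)² = 7.85 × 22.22 ≈ 174.4, rounded up to 175.
- Probability of death by the analysis: 1 − [exp(−14λ) − exp(−44λ)]/(30λ). With λ = ln 2/13.10 = 0.0529 this is 0.761 (control); with 0.65λ it is 0.615 (experimental).
- Patients per arm: 175/(0.761 + 0.615) = 127.2, against 128 stated.
- Inflation: 256/0.85 = 301.2, that is 302 after rounding each arm up to 151.
- With 151 per arm, expected deaths are 151 × 1.376 ≈ 208. Power is Φ(√208 × 0.431/2 − 1.96) ≈ 87%.

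The sample size reproduces and is not in dispute.

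**2. Simple illustration.** Suppose there is no true effect and 1-year survival is 53% in both arms. Removing k experimental patients who died within the year makes that arm's survival 151 × 0.53/(151 − k). For k = 2, 4, 6 and 8 it rises by 0.7, 1.4, 2.2 and 3.0 percentage points.

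**3. False-positive rate.** The protocol gives no ineligibility rate, so k = 3, 5, 8 or 12 experimental exclusions (2% to 8% of 151) is an assumption. Log-rank simulation: 151 per arm, exponential survival with median 13.10 months in both arms, uniform accrual over 30 months, cut at month 44, two-sided level 0.0492, at least 20,000 trials per cell (simulation error 0.1 to 0.2 points). With no exclusions, the one-sided rate favouring TRT is 2.5%.

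| Assumed exclusions | k=3 | k=5 | k=8 | k=12 | Mean HR |
|---|---|---|---|---|---|
| (a) Experimental only, unrelated to outcome | 2.4% | 2.4% | 2.5% | 2.4% | 1.00 |
| (b) k deaths before month 6 from each arm | 2.7% | 2.7% | 2.8% | 3.1% | 1.00 |
| (c) Poor prognosis, k v k/2 rounded down | 3.0% | 3.2% | 3.5% | 4.0% | 0.99 to 0.97 |
| (d) Poor prognosis, experimental only | 3.0% | 3.5% | 4.4% | 5.8% | 0.99 to 0.95 |
| (e) Deaths before month 6, experimental only | 3.8% | 5.0% | 7.1% | 10.8% | 0.98 to 0.91 |

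In (c) and (d), patients are drawn with weight exp(−λT), T being survival time. Counting both tails, the error is 5.1% to 5.7% in (c) and 5.1% to 6.8% in (d), against 5.0% with no exclusions; the unfavourable tail shrinks as the favourable one grows.

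**4. Cost of keeping everyone.** Same design, 20,000 trials per cell. HR is 0.65 in eligible patients, and k ineligible patients per arm gain nothing from TRT.

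| | k=3 | k=5 | k=8 | k=12 |
|---|---|---|---|---|
| Power, all randomised | 85.8% | 85.5% | 83.4% | 81.6% |
| Power, eligible only | 86.1% | 85.9% | 85.5% | 84.3% |

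The loss is 0.3 to 2.7 points.

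**The case against.** The strongest reply is that the wording can be read benignly. Section 11.1.3 enrols patients only once screening is complete and they are deemed eligible, and randomisation follows, so the eligible randomised patients could simply be everyone. The reference in section 7.3.2 to a full analysis set points the same way. This reading fails because section 9.1.2 expressly provides for patients randomised in error, and no other section keeps them in the primary analysis.

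A second reply is that the route to bias is inferred. Section 9.1.2 concerns withdrawal and not analysis sets. Most criteria are screening facts fixed before allocation, such as laboratory values, histology, stage and prior therapy. Who judges eligibility, and whether blind to arm, may be set out in a statistical analysis plan that is not available here. This stands as a limit on the likely size. It does not answer the definition, which the protocol itself fixes.

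A third reply concerns magnitude. The test is two-sided, and total error moves less than the favourable tail, as shown above. The 10.8% figure needs 12 exclusions, all experimental and all early deaths. This also stands: nothing in the protocol points to (d) or (e), which serve only as bounds.

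Finally, the power figures assume HR 0.65 in every eligible patient. If 15% of the experimental arm (23 of 151) also gained nothing because TRT was not completed, an assumed extreme, power is about 75% before any ineligible patient is added. With 3 to 12 ineligible per arm it is about 73% to 67% for all randomised and 73% to 70% for eligible only. The figures above 80% are therefore not assured. That is a separate question from this one, and the cost of the fix stays at about 0.4 to 4 points.

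**Conclusion.** The concern holds. The three definitions agree with one another and contradict the label they carry. As written, a randomised patient later judged ineligible falls outside the primary survival analysis, and that judgement can be made with the arm known. The size of any bias cannot be derived from the protocol: it is negligible if exclusions are unrelated to outcome or balanced between arms, moderate if poor-prognosis patients are removed unevenly, and large only under extreme assumptions. All exclusion counts are assumed. The change should be made because the exclusion is avoidable and serves no need: the endpoint is death from any cause, and survival is already to be followed in all patients.

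**What to change.** - In the synopsis and sections 14.2.2 and 14.4, define the primary set as all randomised patients, analysed in the arm to which they were assigned.
- In section 9.1.2, state that withdrawal for incorrect enrolment ends neither survival follow-up (unless the patient refuses it) nor inclusion in the primary analysis.
- Keep the eligible-only set as a sensitivity analysis, with eligibility judged on pre-randomisation data and, preferably, blind to arm and outcome.
- Align the term full analysis set in section 7.3.2 with the sets defined in section 14.2.

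The cost is wording in four places, plus the alignment of one term. Planned enrolment stays at 302. The downside is the modest dilution shown in step 4 of the working.

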14.3 Methods of statistical analyses

14.3.1 Safety analyses

The frequency and severity of AEs will be compared between the treatment arms using the Pearson's Chisquare and Fisher's exact test as appropriate.

14.3.2 Efficacy analyses

For the primary endpoint, the Cox proportional hazards method will be used to compare survival between the treatment groups. Considering that median overall survival was 12-13 months in the two trials that established chemo-immunotherapy as treatment of ES SCLC, the study is designed to perform the primary survival analyses 14 months after last patient entry (to ensure that all survival data at 1 year are captured), which is a timepoint when we believe that the first signal of an effect of the experimental treatment can be seen. Additional survival analyses will be performed 2-, 3-, 4- and 5-year after last patient entry.

Median OS, PFS and time to progression in the brain will be estimated using the Kaplan-Meier method, and a Cox-model will be used for multivariable analyses adjusting for established prognostic factors in the target population (sex, PS, disease stage, presence of brain metastases and liver metastases) and age. Pearson's Chi-square test will be used to compare response rates (overall and in non-irradiated lesions), frequency of brain metastases, and location of metastases.

All HRQoL scores will be transformed to a scale of 0-100 according to the EORTC QLQ scoring manual. Mean scores will be compared at each assessment timepoint. A difference of 10 points is considered clinically relevant. Primary HRQoL-endpoints are dyspnea, global quality of life and physical function. All other HRQoL-scales will be included in complementary analyses.

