1. PROTOCOL SYNOPSIS

Study title: Randomized phase III trial investigating the survival benefit of adding thoracic radiotherapy (TRT) to durvalumab immunotherapy plus chemotherapy in extensive stage small-cell lung cancer

Protocol version number: 1.0

Clinical phase: Randomized phase III

Study duration: From 2021 until 2028

Investigational therapies and reference therapy:

- Reference therapy: Durvalumab plus carboplatin/etoposide
- Investigational therapy: Durvalumab plus carboplatin/etoposide and TRT

Research hypotheses:

The main hypothesis is that adding TRT to durvalumab plus chemotherapy provides a survival benefit for patients with extensive stage (ES) small-cell lung cancer (SCLC).

Specifically, we hypothesize that:

- combining TRT, durvalumab and chemotherapy is feasible and well tolerated
- adding TRT improves survival, response rates, and PFS
- the patients who benefit the most from the study treatment can be identified through analyses of tissue, blood and stool samples
- toxicity of prophylactic cranial irradiation (PCI) is acceptable in ES SCLC patients who receive durvalumab plus chemotherapy

Objectives:

Primary Objective:

To investigate whether adding TRT to durvalumab plus chemotherapy improves 1-year survival.

Secondary Objectives:

To investigate whether adding TRT improves 2-, 3-, 4- and 5-year overall survival.

To investigate whether adding TRT improves overall response rates, response rates in non-irradiated lesions and PFS.

To investigate whether TRT improves local control.

To compare the frequency and severity of adverse events between the treatment arms.

To compare health related quality of life between treatment arms.

Exploratory Objectives:

To compare the duration of severe adverse events between the treatment arms.

To compare the frequency and timing of brain metastases between treatment arms.

To assess cognitive function in the whole study cohort and compare cognitive function between those who receive PCI and those who do not.

To investigate associations between outcomes of study treatment and biomarkers in tissue, blood and stool (e.g. ctDNA in blood, miRNA, gut microbiome).

Endpoints:

Primary Endpoint:

1-year overall survival

Secondary Endpoints:

2-year, 3-year, 4-year and 5-year overall survival

Overall response rates

Response rates in non-irradiated lesions

Progression free survival

Progression free survival in non-irradiated lesions

Local control rates in the thorax

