4.2.7 TRT in ES SCLC

A randomized phase III trial showed that TRT improves PFS in ES SCLC (HR 0.73, p=0.001), and the PFS curves split immediately after administering TRT. The study did not, however, meet the primary endpoint of improved 1-year survival in the overall population (33% vs. 28%, p=0.066), but there was a significant benefit in terms of 18-months (16% vs 9%, p=0.03) and 24-months survival (13% vs. 3%, p=0.004). Among patients with residual thoracic disease after chemotherapy, there was a significant improvement in OS (HR 0.004). Thus, the role of TRT has been debated, and is not routinely offered in Scandinavia, and was not allowed in the CASPIAN or Impower 133.

[figure not shown]

Figure 3 Progression free survival and overall survival curves from the trial of TRT in ES SCLC (CREST).

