14.1 Endpoints

Primary endpoint

• 1-year overall survival

Secondary endpoints

- 2-year, 3-year, 4-year and 5-year overall survival.
- Overall response rates
- Response rates in non-irradiated lesions
- Progression free survival
- Progression free survival in non-irradiated lesions
- Local control rates in the thorax
- Frequency and severity of adverse events
- Health-related quality of life

Exploratory endpoints

- Duration of severe adverse events
- Frequency and timing of brain metastases
- Assess cognitive function in the whole study cohort and compare cognitive function between patients who receive PCI and those who do not.
- Associations between outcomes of study treatment and biomarkers in tissue, blood and stool (e.g. ctDNA in blood, miRNA and gut microbiome).

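### The primary endpoint is 1-year survival, but the 80% power belongs to a Cox test over all follow-up; at 12 months it is 56–58% with 128 per arm (63–65% with 151).

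*Protocol*

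**What the plan says.** The synopsis gives the primary objective as "To investigate whether adding TRT to durvalumab plus chemotherapy improves 1-year survival". Section 14.1 lists the primary endpoint as "1-year overall survival", with 2-, 3-, 4- and 5-year survival as separate secondary endpoints. Section 5.1 argues for the 1-year measure by name, so the choice looks deliberate.

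Section 14.3.2 names the test: "For the primary endpoint, the Cox proportional hazards method will be used to compare survival between the treatment groups". It places the analysis 14 months after last patient entry, so that every patient's 1-year status is known, and states no truncation at 12 months.

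Section 14.4 bases the sample size on a constant hazard ratio of 0.65, 30 months of accrual and 14 months of further follow-up, and concludes that "to have power of 80% to yield a statistically significant result, 128 patients are required in each treatment group". It gives "1-year survival rates of 53% in the control group and 66% in the experimental group" only as what that hazard ratio corresponds to. No test of those two rates is described and no power is given for one.

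**The concern.** The endpoint, the test and the power statement do not refer to the same quantity. The named endpoint is the probability of being alive at month 12. The named test estimates a hazard ratio from every death up to the data cut, including deaths as late as month 44. If hazards are not proportional, the two can give different answers, and the protocol does not say which one decides the trial.

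The protocol itself gives reason to expect a changing effect. Section 4.2.4 notes that the survival curves in the chemo-immunotherapy trials separate only after about 6 months. Section 4.2.7 reports that the earlier randomised trial of TRT "did not, however, meet the primary endpoint of improved 1-year survival in the overall population" (33% vs 28%, p=0.066), yet showed a difference at 18 months (p=0.03) and 24 months (p=0.004). Those are comparisons at fixed times, not a Cox result, but they show how far the conclusion can depend on the time point.

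Two things are at stake. One is the claim: a significant hazard ratio might be reported as a 1-year benefit that was never tested. The other is power: if the endpoint is analysed as named, the trial does not have the 80% it states.

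**Working it through.** **Inputs (Section 14.4 unless noted).** Control median 13.10 months; HR 0.65; accrual 30 months, taken as uniform; 14 months of further follow-up; 128 per arm; 302 in total, or 151 per arm. Two-sided 5%: "The criterion for significance (alpha) has been set at 5"%, and the test is "2-tailed, which means that an effect in either direction will be interpreted". Allocation is 1:1 (Section 9.1.1). Exponential survival without dropout is assumed.

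**1. Hazards and 1-year survival.**
- Control: λ = ln 2 / 13.10 = 0.05291 per month. Experimental: 0.65 × 0.05291 = 0.03439.
- S(12) = exp(−12λ): 0.530 and 0.662. These match the stated 53% and 66%.

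**2. Reproducing 128 per arm.**
- Probability of death by the cut: 1 − [exp(−14λ) − exp(−44λ)] / (30λ) = 0.761 (control) and 0.615 (experimental), mean 0.688.
- Deaths needed for 80% power: Schoenfeld, 4(1.960 + 0.842)² / (ln 0.65)² = 169; Freedman, (1.960 + 0.842)² × (1.65/0.35)² = 174.
- Patients per arm: 169 / (0.761 + 0.615) = 123; 174 / 1.376 = 127. The stated 128 fits.
- Deaths with 128 per arm: 128 × 1.376 = 176. Power: Φ(√176.1 × 0.4308/2 − 1.960) = Φ(0.898) = 81.5% (Schoenfeld); 80.4% by Freedman.
- The stated experimental median of 20.02 months implies HR 13.10/20.02 = 0.654. Schoenfeld then gives 80.4% and Freedman 79.2%.
- A log-rank simulation of 8,000 trials gives 80.1% at HR 0.654 and 81.6% at HR 0.65.
- Enrolment: 256 / 0.85 = 301.2, rounded up to 302.

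The stated sample size is therefore sound for a Cox or log-rank comparison over all follow-up.

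**3. Power for 53% versus 66% at month 12.** Every patient has at least 14 months of potential follow-up, so without loss the Kaplan-Meier estimate at 12 months is a simple proportion. With p̄ = 0.595:

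Power = Φ{[0.13 − 1.960 √(2 × 0.595 × 0.405 / n)] / √[(0.53 × 0.47 + 0.66 × 0.34) / n]}

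- n = 128: (0.13 − 0.1203) / 0.0608 = 0.160, power 56.4%.
- n = 151: (0.13 − 0.1107) / 0.0560 = 0.344, power 63.5%.
- Unpooled variance with unrounded rates (0.530 and 0.662): 58.3% and 65.4%. A log-log Kaplan-Meier test gives 56–57% and 63–64%. Simulation with 128 per arm gives 56–57%.
- At the final-analysis level of 0.0492 (Section 14.3.4), n = 128 gives 56.1–58.0% with the proportion tests.
- For 80% power: 223 per arm with the rounded rates, 216 with the unrounded.

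**4. Cox model censored at 12 months.** Deaths = 128 × (0.470 + 0.338) = 103. Power = Φ(√103.4 × 0.2154 − 1.960) = Φ(0.231) = 59%. With 151 per arm: 122 deaths, 66%.

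**5. Side by side.**

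| Comparison | 128 per arm | 151 per arm |
|---|---|---|
| Cox, all follow-up (HR 0.65, Schoenfeld) | 176 deaths, 81.5% | 208 deaths, 87% |
| Cox, censored at 12 months | 103 deaths, 59% | 122 deaths, 66% |
| 1-year survival rates | 56–58% | 63–65% |

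**6. Deaths after month 12.** 1 − 103.4/176.1 = 41% of the deaths in the full Cox test fall after the time point named in the endpoint.

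**The case against.** The strongest defence is that the endpoint label is shorthand. The secondary endpoints at 2, 3, 4 and 5 years line up with the later data cuts, so the primary endpoint could mean overall survival analysed at the first cut. The main hypothesis speaks of a survival benefit, and the synopsis defines overall survival from randomisation to death. On that reading the test, hazard ratio, follow-up and power all agree. However, the objective asks about survival at one year, Section 5.1 defends that measure specifically, and Section 14.3.2 justifies the timing by the need for complete 1-year data. If the shorthand reading is what was meant, the endpoint is misnamed and the remedy is the same.

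Three further points stand in part:
- Under the constant hazard ratio assumed in Section 14.4, a ratio below 1 does imply better 1-year survival. The two quantities part only under non-proportional hazards, which the protocol's own background makes plausible.
- The earlier TRT trial is reported in Section 4.2.7 for the overall population only at fixed time points. It does not show a Cox test and a 1-year test disagreeing.
- The primary analysis set is intention to treat (Section 14.2.2), and patients who do not complete treatment stay in it. The 151-per-arm figure of 63–65% is therefore closer to the planned analysis than 56–58%. It is still well short of 80%.

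**Conclusion.** The concern holds and should be fixed. The sample size is correct for a Cox comparison over all follow-up (about 176 deaths, about 80% power with 128 per arm). It does not support the endpoint the protocol names, for which power is 56–58% with 128 per arm and 63–65% with all 302 patients. Truncating the Cox model at 12 months does not rescue it (59% and 66%).

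These figures rest on exponential survival, uniform accrual, no loss to follow-up and the protocol's own effect size. That the Cox test uses all follow-up is inferred from the absence of any stated truncation and from the sample size, but the shortfall on the named endpoint does not depend on that inference. The 128 and 302 are not arithmetic errors.

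**What to change.** Preferred: name overall survival as the primary endpoint, defined from randomisation to death from any cause, using all follow-up at the cut-off 14 months after last patient entry and tested by Cox. Make the Kaplan-Meier difference in 1-year survival the first secondary endpoint. Test, cut-off, sample size and stated power stay as they are. The wording changes are in the synopsis and Sections 5.1, 14.1 and 14.3.2.

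Alternative: keep 1-year survival as primary, specify a test of the Kaplan-Meier difference at 12 months in Section 14.3.2, and restate the power in the synopsis and Section 14.4 as about 56–58% for 128 per arm or 63–65% for 151 per arm.

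Neither option needs extra patients or data, and no change in enrolment is proposed. The cost is an amendment: Section 15.4 requires approval before a substantial change takes effect. Because the trial is open label with an efficacy interim, the change should be justified and made before any comparison of survival by arm is seen.

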14.3.4 Interim analyses

The Safety and data monitoring committee will perform an interim analysis when 2/3 of the target number of patients (n≥85 in both arms) have completed a minimum of three chemotherapy courses (and TRT in the experimental arm). According to the O'Brien-Fleming approach, an alpha of 0.0054 will be allocated to the interim analyses. Consequently, enrolment will be stopped if the survival difference is statistically significant with a 2-sided p≤0.0054. If enrolment continues beyond the interim analysis, the significance level for the primary survival analysis is p≤0.0492.

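### The primary Cox comparison is described without the two randomisation strata, so the test that decides the trial reads as unadjusted: valid, but conservative by an amount that depends on how prognostic the strata are

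*Protocol*

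**What the plan says.** Section 9.1.1 randomises 1:1, "stratifying for presence of liver metastases (yes vs. no), and presence of brain metastases (yes vs. no". Section 6.1 describes these two factors as established prognostic factors.

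Section 14.3.2 sets the primary method: "For the primary endpoint, the Cox proportional hazards method will be used to compare survival between the treatment groups". It names neither strata nor covariates. The synopsis (statistical methods) describes the comparison in the same bare way.

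The next paragraph of 14.3.2 adds that "a Cox-model will be used for multivariable analyses adjusting for established prognostic factors". The listed factors are sex, performance status, disease stage, brain metastases and liver metastases, with age added. This model is not identified as the primary test.

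Section 14.3.4 allows enrolment to stop at the interim if the survival difference reaches p≤0.0054, and otherwise "the significance level for the primary survival analysis is p≤0.0492". It names no model for either look.

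For the design, section 14.4 states that "the calculation is based on a constant hazard ratio of 0.65" and that, "to have power of 80% to yield a statistically significant result, 128 patients are required in each treatment group".

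**The concern.** The protocol balances the arms on two factors because they predict survival, then describes a primary comparison that does not use them. Balancing on prognostic factors makes the treatment estimate vary less from trial to trial than an unadjusted model assumes. The unadjusted standard error is then a little too large and the test rejects too rarely. In a Cox model, leaving out a prognostic factor also moves the HR toward 1, because the marginal HR is closer to 1 than the within-stratum HR.

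Two things are at stake. The first is efficiency: the design aims at 80% power and has little to spare at 128 per arm. The second is clarity: two Cox analyses of survival are planned, and neither the interim boundary nor the final significance level is tied to a fully described model.

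**Working it through.** **Step 1. Reproduce the sample size as a plain two-group comparison.**

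Inputs from section 14.4: HR 0.65, medians 13.10 and 20.02 months, two-sided 5%, 80% power, 30 months' accrual, 14 months' further follow-up.

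- Event probability with uniform accrual: p = 1 − (e^(−14λ) − e^(−44λ)) / (30λ), with λ = ln 2 / median. Control 0.761, experimental 0.617, mean 0.689.
- Freedman events: (1.65/0.35)² × (1.960 + 0.842)² ≈ 174.4, rounded up to 175.
- Patients per arm: 175 / (2 × 0.689) = 127.0. Lachin-Foulkes gives 129.7.
- Inflation for 15% loss: 256 / 0.85 = 301.2, rounded up to 302.

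The stated 128 per arm and 302 in total reproduce. At 128 per arm, expected events are 128 × (0.761 + 0.617) ≈ 176.4. Schoenfeld power is 81.6% at 5% and 81.4% at 0.0492.

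**Step 2. Power with and without the strata.**

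The protocol gives neither the prevalence nor the prognostic strength of the factors, so these are assumptions: liver metastases 40%, brain metastases 15%, and the prognostic HRs shown. Trials were simulated with allocation balanced within the four strata, exponential survival and the planned accrual and follow-up. The test is two-sided at 5%. The size of 151 per arm is 302 / 2, the planned enrolment.

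| Liver / brain HR | 128 per arm: unstratified vs stratified | Gain (points) | 151 per arm: unstratified vs stratified | Gain (points) |
|---|---|---|---|---|
| 1.3 / 1.2 | 81.3 vs 81.5% | 0.2 | 86.6 vs 86.2% | −0.4 |
| 1.5 / 1.3 | 79.1 vs 79.7% | 0.6 | 85.3 vs 85.8% | 0.5 |
| 2.0 / 1.5 | 75.9 vs 79.4% | 3.5 | 82.3 vs 85.2% | 2.9 |
| 2.5 / 1.5 | 73.1 vs 78.6% | 5.5 | 79.0 vs 84.1% | 5.1 |

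The first two rows show no clear difference: with 2,000 trials the simulation error on a single power figure is about 0.9 points. Separate runs of the last two rows gave gains of 3.7 and 6.7 points at 128 per arm (4,000 trials), and 3.2 and 6.2 points at 151 per arm (3,000 trials). The top of the range is therefore uncertain by about a point.

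**Step 3. Hazard ratio and type I error.**

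A further simulation used 128 per arm, within-stratum HR 0.65 and 2,000 trials per scenario. Type I error was taken from matching runs with HR 1.

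| Assumed factors (prevalence, HR) | HR unadjusted vs stratified | Type I error unadjusted vs stratified |
|---|---|---|
| Liver 40%, 1.3; brain 15%, 1.2 | 0.652 vs 0.649 | 4.4 vs 4.8% |
| Liver 40%, 1.6; brain 15%, 1.3 | 0.656 vs 0.647 | 4.2 vs 5.6% |
| Liver 40%, 2.0; brain 20%, 1.6 | 0.671 vs 0.651 | 3.8 vs 4.5% |
| Liver 40%, 2.5; brain 30%, 2.0 | 0.685 vs 0.647 | 3.2 vs 4.8% |

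Simulation error on type I error is about 0.5 points. The unadjusted HR is nearer 1 in every row, and the unadjusted test becomes more conservative as the factors become more prognostic. Entering the two factors as covariates instead of strata gave power of 81.0, 81.8, 78.8 and 79.8%, against 80.6, 79.7, 74.8 and 69.4% unadjusted. The last row combines assumptions more extreme than those in step 2.

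**The case against.** The strongest reply is that the protocol is silent rather than wrong. It nowhere calls the primary model unadjusted or unstratified, strata and covariates are often settled in an analysis plan that is not shown, and a Cox model containing both factors is planned anyway. The first part stands: a reader might infer that the protocol deliberately excludes the factors, and no sentence says so. But the protocol itself chose the primary method. It describes two Cox analyses, ties the primary endpoint to the one without the factors and puts the factors in the other. That leaves an unadjusted primary test as the natural reading.

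Three stronger inferences are tempting and are not supported:

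- **The sample size is wrong.** It reproduces for an unadjusted two-group comparison.
- **The false-positive rate is raised.** The simulated type I error of the unadjusted test is below 5%.
- **The unadjusted HR is biased.** Section 14.4 gives 0.65 together with overall medians and 1-year rates, so an unadjusted HR matches the stated design. It estimates a marginal quantity, which is simply nearer 1 than the within-stratum one.

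It is also fair that the primary set is all eligible randomised patients, about 151 per arm, not 128. At that size the unstratified test keeps about 79 to 87% power in the step 2 scenarios. That assumes the full effect and no loss to follow-up; dilution by patients who do not complete treatment would lower both tests. The gap between the tests is similar at either size.

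**Conclusion.** The point holds as an efficiency and clarity improvement, not as an error of validity. The direction is firm: after stratified randomisation on prognostic factors, an unadjusted Cox test is conservative and its HR is somewhat closer to 1.

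The size is not firm, because it rests on prevalences and prognostic HRs that the protocol does not give. With liver metastases in 40% and brain metastases in 15%, it is about 0 to 1 point of power for HRs up to 1.5/1.3, and about 3 to 6 points for a liver HR of 2.0 to 2.5. A reader might take a material loss of power as established; it is not, since under mild assumptions there is no visible gain from stratifying. The change is still worth making, because it costs almost nothing and protects the design if the factors are strongly prognostic.

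**What to change.** In section 14.3.2 and the synopsis, state that:

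- the primary Cox test is stratified by (or adjusted for) presence of liver metastases and presence of brain metastases, using the values recorded at randomisation;
- this model is the confirmatory one at p≤0.0492, and the same model governs the interim at p≤0.0054 (with a cross-reference in section 14.3.4);
- the unadjusted Cox model is a sensitivity analysis, and the wider multivariable model remains supportive.

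The change should be made before any survival comparison by arm has been seen, so that the choice between models cannot depend on the result. It costs a few sentences in the protocol and the matching text in the analysis plan. Both factors are already recorded for randomisation, so no new data or patients are needed.
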